6.1. PRIMARY EFFICACY ENDPOINT

The primary endpoint will evaluate the percent of successful terminations of life-threatening VT or VF in subjects who are enrolled in compliance with the protocol-defined entry criteria and are treated with either model of the Jewel EP Lab System. The endpoint will be achieved if the lower confidence limit exceeds the performance goal of 62% using a one-sided exact lower 97.4% confidence bound at one of three testing points. These conditions ensure that performance will be in line with previously published randomized controlled trial results on a relevant comparator, the ZOLL LifeVest, which is the only commercially approved WCD in Europe or the United States. A sequential method of testing will be used to evaluate conversion success. If the Jewel EP Lab System is NOT used to deliver a defibrillation shock during the EP procedure, the subject will not be included in the treatment analysis.

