For the calculation of sample size, this study will use an anticipated first shock conversion success rate of 87.5% in the EP Lab Study with a performance goal of 62%, the same as the first shock success rate seen in VEST. The performance of the Jewel will be considered acceptable if the lower confidence limit exceeds the performance goal of 62% (green line in the graph on page 24).

The sample size for this study is a maximum of 24 subjects. Subjects can be treated with either the ES-1 or the ES-2 model of the Jewel EP Lab System, as the devices are representative of each other. This sample size is based on a group sequential design measuring the observed proportion of successful life-threatening VT or VF terminations. The group sequential design uses a Pocock alpha spending function and allows for testing after 12, 18, and 24 subjects are enrolled. The design controls the overall Type I error rate at 5%. In line with the Pocock alpha spending function, a one-sided lower 97.4% exact confidence bound will be calculated using the exact binomial (Clopper-Pearson) method at each testing point.

Primary Endpoint Analysis:

Upon completion of the Jewel EP Lab Study, all clinical data from both the ES-1 and ES-2 models of the Jewel EP Lab System will be pooled, as the devices are representative of each other. The primary endpoint will evaluate the percent of successful terminations of life-threatening VT or VF in subjects who are in subjects who are enrolled in compliance with the protocol-defined entry criteria and treated with the Jewel EP Lab System (either ES-1 or ES-2 model).

Using the VEST RCT results for the first shock success as a guide, the performance goal of 62% was established for the Jewel EP Lab Study. The endpoint will be achieved if the lower confidence limit exceeds the performance goal of 62% using a one-sided lower 94.5% exact confidence bound at one of the three testing points.

These conditions ensure that performance will be in line with previously published randomized controlled trial results on a relevant comparator, the ZOLL LifeVest which, is the only commercially approved WCD in Europe or the US. The method for testing the conversion success will follow these steps:

1. If after attempting to convert the first 12 subjects, all subjects have been successfully converted (100% conversion rate) the trial will be stopped and deemed a success. Otherwise, continue to Step 2.

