2. If conversion is less than 100% after 12 total subjects, enroll six (6) additional subjects for a total of 18 subjects. If 17 out of the 18 are successfully converted (94.4% conversion rate), or if 16 out of the 18 are successfully converted (88.0% conversion rate), the trial will be stopped and deemed a success. Otherwise, continue to Step 3.
3. Enroll the final six (6) subjects for a total of 24 subjects. If after attempting to convert 24 subjects, 21 of the 24 are successful (87.5% conversion rate), the trial will be deemed a success.

A 100% conversion rate with 12 subjects results in a one-sided lower 97.4% exact confidence bound of approximately 73.7% which exceeds the 62% performance goal.

[figure not shown]
With a sample size of 18 subjects with 1 failure, the conversion rate is 94.4% with a one-sided lower 97.4% exact confidence bound of approximately 72.8% which also exceeds the 62% performance goal.

With a sample size of 18 subjects with 2 failures, the conversion rate is 88.9% with a one-sided lower 97.4% exact confidence bound of approximately 65.4% which also exceeds the 62% performance goal.

With a sample size of 24 subjects with 3 failures, the conversion rate is 87.5% with a one-sided lower 97.4% exact confidence bound of approximately 67.8% which also exceeds the 62% performance goal.

All of these scenarios result in a successful trial as the one-sided lower 97.4% exact confidence bound is above the performance goal of 62%. If at any point during the course of this study there are more than three (3) failures to convert a shockable rhythm (life-threatening VT or VF) due to the Jewel, the study will be stopped and deemed unsuccessful.

The graph below summarizes the group sequential study design, conversion success, and results of the one-sided lower 97.4% exact confidence bound.

Overall Type I Error Discussion:

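### The failure stop counts only failures attributed to the Jewel, but the endpoint counts every failed Jewel shock, and Sections 6.1 and 11.1 imply different final cut-offs

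*Combined protocol and SAP*

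**What the plan says.** Section 6.1 gives a general criterion: "The endpoint will be achieved if the lower confidence limit exceeds the performance goal of 62% using a one-sided exact lower 97.4% confidence bound". Section 11.1 (Primary Endpoint Analysis) then sets out steps at 12, 18 and 24 subjects: 12/12, then 16/18 or 17/18, and finally "If after attempting to convert 24 subjects, 21 of the 24 are successful (87.5% conversion rate), the trial will be deemed a success".

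A separate stop in Section 11.1 applies at any time. With more than three "failures to convert a shockable rhythm (life-threatening VT or VF) due to the Jewel, the study will be stopped and deemed unsuccessful".

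Sections 6.1, 8.2, 9 and 11.1 define who is counted in the primary analysis: every subject who meets the entry criteria and received a Jewel shock. None of them makes a failure conditional on its cause. No section says what *due to the Jewel* means, who decides it, or when. Section 6 describes a non-blinded study in which the sponsor and the principal investigator monitor safety, and it names no adjudicator of failed shocks.

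**The concern.** The endpoint and the stop count different things. A failed shock put down to use error, patch placement or the patient's condition lowers the success rate but may not move the study towards its failure stop.

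What follows depends on which final cut-off is binding, so the two consequences are alternatives:

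- **Step 3 binding (21/24).** A fourth failure of any cause makes success unreachable, but the stop may not fire. More subjects then receive an investigational shock in a study that can no longer succeed. Section 11.1 itself says that the sequential design is there to reduce the number of subjects put at risk.
- **Section 6.1 binding (97.4% bound above 62%).** The result 20/24 meets the criterion. The only text that expressly calls four failures unsuccessful is the stop, and the stop depends on attribution.

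**Working it through.** **Inputs.** From the plan: performance goal 62%, assumed true rate 87.5%, one-sided exact 97.4% bound, looks at 12, 18 and 24 (taken here as treated subjects), stop at the fourth attributed failure. Not in the plan, so assumed: a share q of failures attributed elsewhere, independently for each failure, shown for 0, 10%, 25% and 50%, plus the extreme where the stop never fires.

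**Step 1: the plan's own bounds.** The Clopper-Pearson lower bound for x successes in n is the 0.026 quantile of Beta(x, n − x + 1).

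| Result | Plan | Recomputed |
|---|---|---|
| 12/12 | 73.7% | 73.8% |
| 17/18 | 72.8% | 72.9% |
| 16/18 | 65.4% | 65.5% |
| 21/24 | 67.8% | 67.8% |
| 20/24 | not given | 62.8% |
| 19/24 | not given | 58.0% |

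The plan's figures reproduce to within 0.1 point. The smallest counts that pass the Section 6.1 criterion are 12, 16 and 20. Sections 6.1 and 11.1 therefore agree at the first two looks and differ only at the last, 20/24 against 21/24.

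**Step 2: enumeration.** Each treated subject is a success with probability p, an attributed failure with probability (1 − p)(1 − q), or a failure attributed elsewhere with probability (1 − p)q. All paths through the three looks were summed exactly.

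**Step 3: if 21/24 is binding.** Success by look at p = 62% is 0.00323 + 0.01085 + 0.00191, or 1.60%. At p = 87.5% it is 0.20142 + 0.40955 + 0.09415, or 70.5%. Neither depends on q, because a study with four failures cannot succeed anyway. What changes is the expected number treated. Paths are identical up to the fourth failure, so the mean number treated after it is the expected number at q minus the expected number at q = 0.

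| Share attributed elsewhere | Expected treated, p = 62% | After 4th failure | Expected treated, p = 87.5% | After 4th failure |
|---|---|---|---|---|
| 0 | 10.43 | 0 | 17.01 | 0 |
| 10% | 11.55 | 1.1 | 17.51 | 0.5 |
| 25% | 13.66 | 3.2 | 18.14 | 1.1 |
| 50% | 18.36 | 7.9 | 18.84 | 1.8 |
| stop never fires | 23.90 | 13.5 | 19.13 | 2.1 |

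**Step 4: if Section 6.1 governs.** The result 20/24 adds to the final-look success probability only if the stop has not fired, that is, if at least one of the four failures is attributed elsewhere. That has probability 1 − (1 − q)^4: 0.344, 0.684 and 0.9375 for q = 10%, 25% and 50%.

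- The extra probability from 20/24 with no stop is 0.01340 − 0.00191 = 0.01149 at 62%, and 0.22630 − 0.09415 = 0.13215 at 87.5%.
- Example, q = 25%: false success = 0.01598 + 0.684 × 0.01149 = 2.38%; power = 0.70511 + 0.684 × 0.13215 = 79.5%.

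| Share attributed elsewhere | False success at 62% | Power at 87.5% |
|---|---|---|
| 0 | 1.60% | 70.5% |
| 10% | 1.99% | 75.1% |
| 25% | 2.38% | 79.5% |
| 50% | 2.68% | 82.9% |
| stop never fires | 2.75% | 83.7% |

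Section 11.1 also mentions a 94.5% bound in one sentence. The working uses 97.4%, the level in Section 6.1 and in all the plan's worked examples. At 94.5% the bound for 20/24 is 66.3%, so that result would pass there too.

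**The case against.** The strongest reply is that the specific governs the general. Section 6.1 itself refers to a sequential method of testing, Section 11.1 says that testing follows the listed steps, those end at 21/24, and the worked scenarios show three failures in 24 but never four. On that reading 20/24 is not a success, whatever anyone decides about cause. This stands as the more natural reading, but it does not settle the matter: Step 3 says when the study succeeds and does not say that 20/24 fails, and Section 6.1 declares success whenever the bound exceeds 62%. It also leaves the continued-enrollment consequence untouched.

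Second, the phrase may be loose wording for a failed Jewel shock as opposed to a failed rescue shock. That is possible, since Section 8.2 allows one Jewel shock per procedure and the rescue defibrillator after it. No section says so, and if it is what was meant, the edit costs nothing.

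Third, continued exposure has safeguards. Subjects are already scheduled for procedures in which VT or VF may occur or be induced, a rescue defibrillator is ready, safety is monitored continuously, and the sponsor can terminate the study (Sections 6, 8.2, 9). These limit the harm. They do not supply a rule that ends the study when success is out of reach.

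A reader might infer that an unblinded team could, by attribution alone, turn a failed study into a success. The documents do not support that. They assign attribution to nobody, and a changed verdict also requires Section 6.1 to prevail over Step 3.

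**Conclusion.** The point holds: the stop is wrong as written, because it counts failures differently from the endpoint and because Section 6.1 and Step 3 imply different final cut-offs.

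With 21/24 binding, the cost is avoidable exposure. At attribution shares of 10% to 50% it averages 1.1 to 7.9 subjects if the true rate is 62%, and 0.5 to 1.8 at the planned 87.5%. False success and power do not move. With Section 6.1 binding, the verdict at 20/24 turns on an undefined judgement.

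Two stronger inferences should be resisted. The Type I error is not pushed past its limit: at the 97.4% level it never exceeds 2.75%, against the stated 5%. And 2.75%, 83.7% and 23.9 treated subjects are extremes in which the stop never fires, not expected effects. All intermediate figures rest on the assumed attribution share and on independent attribution, since the plan gives neither.

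**What to change.** In Section 11.1, delete *due to the Jewel* so that every failed Jewel shock in the primary analysis counts towards the stop. Report the suspected cause of each failure (device deficiency, use error, patient factors) descriptively. Then reconcile Section 6.1, Step 3 and the stop so that one final cut-off applies and the study stops once that cut-off cannot be reached.

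This is a short edit, but it touches both sections. Its costs are:

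- A failure from an unrelated cause counts towards the stop, as it already does in the endpoint.
- Keeping the limit at more than three failures makes 20/24 a failure in all cases. That loses no power relative to Steps 1 to 3, but exact power at 87.5% is then 70.5%, so the 90% stated in Section 11.1 has to be restated.
- If 20/24 were chosen instead, the matching limit would be more than four failures. False success would be 2.75% and power 83.7%, which is still short of 90%.

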The group sequential design of the Jewel EP Lab Study is meant to control the overall Type I error rate with 90% power. This design uses a Pocock alpha spending approach which controls the overall Type I error rate at 5%. The group sequential design of the Jewel EP Lab Study is being used in order to reduce the number of subjects put at risk through early stopping rules, while still providing sufficient data to demonstrate the effectiveness of the Jewel EP Lab System to successfully convert life-threatening VT and VF. Preliminary testing points and alpha expenditures were estimated using SAS version 9.3 which employs a normal approximation to designing sequential trials. The alpha spent at each testing point was used to determine the confidence level of the exact lower confidence bound. These confidence levels were then used to adjust the testing points to accommodate exact methods rather than the normal approximation. Simulations of 3000 trials of size 24 were used to confirm that the Type I error rate was controlled at the 5% level.

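### The design is described as having 90% power, but the written stopping rules give 70.5% exact power at the planned 87.5% conversion rate

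*Combined protocol and SAP*

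**What the plan says.** All of this stands in section 11.1 of the combined protocol and SAP.

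- **Planning rates:** "this study will use an anticipated first shock conversion success rate of 87.5% in the EP Lab Study with a performance goal of 62" (per cent).
- **Looks:** "The group sequential design uses a Pocock alpha spending function and allows for testing after 12, 18, and 24 subjects are enrolled".
- **Bound:** "a one-sided lower 97.4% exact confidence bound will be calculated using the exact binomial (Clopper-Pearson) method at each testing point".
- **Decision steps (Primary Endpoint Analysis):** success at the first look needs 12 of 12, and at the second look 16 or 17 of 18. At the last look, if "21 of the 24 are successful (87.5% conversion rate), the trial will be deemed a success". More than three failures due to the device at any time makes the study unsuccessful.
- **Error rates:** the closing part of the section, on type I error, states "The group sequential design of the Jewel EP Lab Study is meant to control the overall Type I error rate with 90% power". The preliminary testing points came from a normal approximation in SAS and were then moved to suit exact methods.
- **Check of the final rule:** "Simulations of 3000 trials of size 24 were used to confirm that the Type I error rate was controlled at the 5% level".

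The section describes no check of power for the final rule, and names no rate other than 87.5% to which the 90% could refer.

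**The concern.** The final look requires an observed rate of 87.5%, which is the same as the rate assumed to be true. A cut-off placed at the expected value is passed only a little more than half the time, so the interim looks would have to supply much of a 90% power. With only 12 and 18 subjects and strict interim cut-offs, that looked unlikely. The order of work described in the plan also leaves a gap: power could have been computed under the normal approximation and never recomputed after the cut-offs were changed.

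The 90% is the only power figure that the ethics committee, the health authority and the sponsor are given. If it is too high, they understate the chance that a device performing as planned fails its primary endpoint, and a miss could be given more weight against the device than it deserves.

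**Working it through.** **Inputs, all from section 11.1.** Goal 62%; anticipated rate 87.5%; looks at 12, 18 and 24; success at 12/12, at least 16/18, or at least 21/24; failure at the fourth non-conversion. Each subject counted has received one shock, and outcomes are independent with a common rate p.

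**The plan's bound, reproduced first.** For 12/12 the one-sided 97.4% Clopper-Pearson bound is 0.026^(1/12) = 0.738, against about 73.7% in the plan. The confidence level also fits the stated design: a one-sided 5% Pocock boundary with looks at 12, 18 and 24 has a nominal level of 0.0258 per look. The inputs are therefore read as the plan intends.

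**Exact power at p = 0.875**

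1. Look 1: 0.875^12 = 0.2014.
2. Look 2, reached with 11/12 or 10/12:
   - P(11/12) = 12 × 0.875^11 × 0.125 = 0.3453, then at least 5 of 6 (0.8335): 0.2878
   - P(10/12) = 66 × 0.875^10 × 0.125^2 = 0.2713, then 6 of 6 (0.4488): 0.1218
   - Sum, allowing for rounding: 0.4095.
3. Look 3, reached with 15/18:
   - P(15/18) = 816 × 0.875^15 × 0.125^3 = 0.2150
   - Less paths already stopped at 12/12: 0.2014 × 20 × 0.875^3 × 0.125^3 = 0.0053, leaving 0.2098
   - Then 6 of 6 (0.4488): 0.0941.
4. Total: 0.2014 + 0.4095 + 0.0941 = **0.705** (0.7051 before rounding).

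**Exact type I error at p = 0.62, same steps.** 0.0032 + 0.0108 + 0.0019 = **0.016**.

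The stop at more than three failures changes neither figure, because 21/24 already allows at most three. A simulation of 400,000 trials per rate gave 70.7% and 1.6%.

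**Power of the written rules by true rate**

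| True rate | Exact power |
|---|---|
| 85% | 57.5% |
| 87.5% | 70.5% |
| 90% | 82.5% |
| 92.5% | 92.0% |

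Power of 90% needs a true rate of about 91.9%.

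**Attempts to recover 90% at a true rate of 87.5%**

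| Reading | Type I error | Power |
|---|---|---|
| Written steps: 12/12, 16/18, 21/24 | 1.6% | 70.5% |
| All results clearing the 97.4% bound: 12/12, 16/18, 20/24 | 2.7% | 83.7% |
| All results clearing the 94.5% bound, also named in section 11.1: 11/12, 15/18, 20/24 | 6.2% | 87.8% |
| Best cut-offs at 12/18/24 with type I error at most 5%: 11/12, 16/18, 20/24 | 4.25% | 85.1% |

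Normal-approximation Pocock designs with these looks gave 77.8%, 84.1%, 85.5% or 97.4%, depending on the variance used. The only calculation that came near 90% was a single-look normal approximation at n = 24 and one-sided 5%. There the standard errors are √(0.62 × 0.38/24) = 0.0991 and √(0.875 × 0.125/24) = 0.0675, so power is Φ[(0.255 − 1.645 × 0.0991)/0.0675] = Φ(1.36) = 91.4%. That calculation ignores the interim looks and the exact rules. Whether it is the source of the 90% cannot be told from the plan.

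**The case against.** The strongest objection is that 70.5% depends on one reading of the plan. Sections 6.1 and 11.1 also define success as a lower bound above 62% at one of the looks, and 20/24 has a 97.4% exact bound of 62.8%. The failure stop counts only failures due to the device, so it need not exclude every 20/24 result. On that reading power is 83.7% and the shortfall is about 6 points rather than 19.5. This stands as a reason to give both figures. It does not rescue the 90%, and the written third step asks for 21/24.

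The wording describes an intention, and the study is called a feasibility study. The 90% may thus be a design target that was not updated. That may explain the figure, but it remains the only power given, it stands beside the final rules, and the study has a formal pass/fail endpoint.

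Type I error is controlled: 1.6% is below 5%, so the plan's statement on that is true. Nor is unspent type I error the whole explanation for the low power. Better cut-offs could recover at most 85.1 − 70.5 = 14.6 of the 19.5 points. The other 4.9 cannot be recovered with these looks and 24 subjects. How a failed study would be interpreted is conjecture, since the plan says only that it would be deemed unsuccessful.

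**Conclusion.** The concern holds. The stated 90% power is wrong for the design as written: exact power at the planned 87.5% is 70.5%, a shortfall of 19.5 points. The chance of missing the endpoint with a device that performs as planned is 29.5%, nearly three times the 10% implied. No set of success cut-offs at these looks, with exact type I error at or below 5%, reaches 90%.

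The result assumes independent outcomes with a common rate, the numbered steps as the decision rule, and looks counted in subjects who received a shock. If the cap of 24 instead counts enrolled subjects, the roughly 30% whom section 8.2 expects to need no shock would lower power further.

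**What to change.** In section 11.1, replace the 90% statement with the exact operating characteristics of the written rule: type I error 1.6% at 62%, power 70.5% at 87.5%, and 90% power only at a true rate near 92%. Report the exact binomial enumeration, with type I error and power together, in place of the statement on the 3000 simulated trials; the enumeration needs no simulation.

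Reconcile the third step and the failure stop with the bound-based definition of success. If 20/24 is to count as success, state 83.7% power and 2.7% type I error instead.

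The cost is protocol and SAP wording, with no extra subjects. The stated power becomes less favourable, and the sponsor should record whether it accepts that at a maximum of 24.

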12. ADMINISTRATIVE CONSIDERATIONS

12.1. INVESTIGATORS AND STUDY ADMINISTRATIVE STRUCTURE

The Investigator should ensure that all persons assisting with the trial are adequately qualified and informed about the protocol, any amendments to the protocol, the study treatments, and their trial-related duties and functions. The Investigator must maintain a list of sub-investigators and other appropriately qualified persons to whom he/she has delegated significant trial-related duties.

12.2. INDEPENDENT ETHICS COMMITTEE (IEC) APPROVAL

The Investigator will not begin the study until the protocol and PIC have been approved by the IEC. As the product is investigational, national health authority approval is also required. The IEC will also review and approve all advertisements, if applicable. The IEC approval will be documented in writing and sent to the Investigator. The Investigator will forward a copy of the IEC approval document to the Sponsor. Any amendments to the protocol must also be approved in writing by the IEC, prior to implementation by the Investigator, except where necessary to eliminate an immediate hazard to study participants.

The Investigator will submit a progress report to the IEC at intervals as established by the IEC. The Investigator will retain a copy of this report in the Investigator's Site File.

